4.1 Description of Study Design

This study will use a scientifically robust, mixed-methods, two-arm cluster-randomized study design. Study subjects are not NYULH employees or patients. We will implement a tobacco use clinical reminder for outpatient psychiatrists practicing at the VA New York Harbor Healthcare System (N = 20). Half of the psychiatrists will receive a reminder that encourages the psychiatrist to offer cessation medications and referral to cessation counseling to patients interested in quitting (Opt-In Reminder). The other half will receive a clinical reminder that includes a standing NRT order and a referral to cessation counseling that will automatically generate unless the provider actively opts-out (Opt-Out Reminder). Prior to implementation of the reminders, psychiatrists in both arms will receive a one-hour training on tobacco treatment and individual education outreach to demonstrate the clinical reminder and answer questions (academic detailing).

[figure not shown]
We will use VA administrative data extracted on all patient visits with a participating psychiatrist 6 months before and after implementation to calculate the study's primary outcomes: 1) the percent of patients screened for smoking, 2) the percent of smokers prescribed a cessation medication and 2) the percent of smokers referred to counseling. To assess intervention fidelity, we will use training logs to track psychiatrist attendance at group and academic detailing trainings. Over the intervention period, we will also conduct post-visit surveys with a cluster sample of 400 patients (20 per psychiatrist) to assess psychiatrist fidelity to the 3 A's approach. At the end of the intervention period, we will conduct semi-structured interviews with 12-14 psychiatrists (6-7/arm) asking about their perceptions of the intervention components. We will also analyze implementation observations (e.g., training observations, reflection memos) and documents (e.g., meeting minutes) for implementation barriers and facilitators. At six months, we will survey the clustered 400-patient sample again to evaluate the study's secondary outcomes: 1) patient use of cessation treatment in the prior 6 months and 2) self-reported 7-day abstinence at 6 months.

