One month before implementation of the provider training and reminders, all psychiatrists in the facility will be notified of the study at a required staff meeting. Psychiatrists will have the option at the meeting to ask questions and have the opportunity to opt-out of study participation. Psychiatrists will also have the opportunity to ask questions one-on-one with [name] before deciding whether to participate. Psychiatrist turn-over is low at the facility; however, during recruitment we will ask psychiatrists if they plan to leave in the next 6 months and only enroll those who have no plans to leave. When [name] used this approach to provider participation in a study implementing a new tobacco treatment model in VA NYHHS primary care clinics, 50 of 51 primary care providers participated.[24] In the ongoing CHORD study, led by [name], no primary care providers opted out of participation. We conservatively anticipate that 20 of 24 psychiatrists at the VA NYHHS will participate.

CONFIDENTIAL

Psychiatrists who do not opt-out of participation will be randomized to one of the two study arms, stratified by their patient panel size and by the number of patients who smoke (captured as a health factor in the EHR) in their prior-year panel. Randomization will be supervised by the study's statistician. Psychiatrists who opt-out of study participation will receive the opt-in clinical reminder as a part of their routine care, but their performance will not be included in study analyses.

Figure 1. Overview of study design

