9.2.2 Analysis of the Primary Efficacy Endpoint(s)

AIM 1: Estimate the effects of an Opt-Out versus Opt-In Tobacco Treatment System on the proportion of mental health patients who are screened and treated for tobacco use by their psychiatrist.

Based on administrative data, we will categorize the proportion of patients seen by a participating psychiatrist in each group who were: (1) screened for tobacco use by the psychiatrist, (2) among smokers, received a cessation medication prescription from the psychiatrist, and (3) among smokers, referred to cessation counseling by the psychiatrist. We will use generalized linear mixed effect models (GLMMs) to compare these screening and treatment rates between groups. For all analyses, sensitivity analyses will be used to evaluate the impact on results from missing data and subject dropout. Specifically, missingness will be handled by creating a separate category, or removed by multiple imputation (MI). An intent-to-treat (ITT) approach will be compared with a complete-case only method.

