AIM 2: Assess intervention fidelity, provider perceptions, and barriers and facilitators to implementation: For intervention fidelity, we will use descriptive statistics to summarize the patient post-visit survey data to calculate the proportion of patients seen by a participating psychiatrist in each study arm who were asked about smoking, offered medications, offered counseling referral, and (among those offered) the proportion of patients who accepted medications and referral. We will also summarize training fidelity logs (the proportion of psychiatrists who attended the trainings and received an academic detailing session). To assess provider perceptions quantitatively, we will summarize provider survey data using descriptive statistics (means, standard deviations) to understand providers' attitudes and beliefs regarding treating their patients for tobacco. For our qualitative data analysis (interviews, observations, reflection memos, meeting minutes), we will use a three-step coding process for each data source. First, two investigators will individually read a sub-sample of data (e.g., 3 interviews) to identify preliminary inductive codes, then meet to achieve consensus on coding the sub-sample and create the first draft of a code book. Second, the investigators will individually apply the codebook to a second sub-sample of data, and meet to achieve coding consensus on the second sub-sample to create final codebook for the data source. Third, once all data are coded, the investigators will meet to complete more focused coding to identify code clusters, relationships among codes, and common themes. Once all data sources are coded, we will also use group consensus meetings to look for themes across the four main data sources.

AIM 3: Estimate the effect of the Opt-Out Reminder versus the Opt-In Reminder on the use of cessation treatment and self-reported abstinence among mental health patients who smoke: We will use a similar analytic approach as in Aim 1. We will first categorize each patient as: (1) having achieved or not achieved 7-day abstinence 6 months after their psychiatry visit and (2) having used or not use any type of cessation treatment in the 6 months after their visit. This will estimate use of treatment and abstinence rates for each study arm. We will use GLMMs to compare these two outcomes between groups. Sensitivity analyses will be used to evaluate the impact on results

CONFIDENTIAL

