9.3 Sample Size

We aim to enroll all practicing psychiatrists at the VA New York Harbor Healthcare System, but have conservatively estimated that 20 will enroll. This sample will allow us to study provider behavior during approximately 4,000 unique patient visits over 6 months. We calculated the level of power this will provide us to find a significant group effect on the proportion of patients prescribed a cessation medication by their psychiatrist (primary outcome 2). Our power calculation varied the intraclass correlation (ICC) of 0.05-0.15 based on a cluster-randomized trial of preventive care in primary care practices.⁵⁴ We estimate that 10% of patients in Arm 1 will receive a prescription.¹⁵ With the smallest ICC of 0.05, a type I error of 5%, and 80% power, 4,000 visits will provide us with enough power to detect a 21% or greater prescription rate in Arm 2. With the largest ICC of 0.15, a type I error of 5%, and 80% power, 4,000 visits will provide us with enough power to detect a 29% or greater prescription rate in Arm 2.

10 Ethics/Protection of Human Subjects

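### Arms are compared by GLMM on about 20 randomised psychiatrists with no small-sample method stated; an uncorrected test would reject at roughly 6–8.5%, not 5%

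*Combined protocol and SAP*

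**What the plan says.** Section 4.1 makes the psychiatrist the unit of allocation: participants are "randomized to one of the two study arms, stratified by their patient panel size and by the number of patients who smoke". Half go to each arm. Section 9.3 puts the number at 20 ("have conservatively estimated that 20 will enroll") and expects "approximately 4,000 unique patient visits over 6 months".

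The method for the three primary outcomes, in Section 9.2.2 under Aim 1, is: "We will use generalized linear mixed effect models (GLMMs) to compare these screening and treatment rates between groups". For the two Aim 3 outcomes the same section says: "We will use GLMMs to compare these two outcomes between groups".

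Section 9 does not say whether estimation is by full or restricted likelihood, whether the test is Wald, likelihood ratio or F, or which degrees of freedom apply. It mentions no small-sample correction, permutation test or cluster-level analysis. The 5% error rate appears only in Section 9.3, for example: "With the smallest ICC of 0.05, a type I error of 5%, and 80% power".

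**The concern.** The reminder type varies between psychiatrists, never within one. Information about the arm effect is therefore limited by the 20 psychiatrists, and 4,000 visits do not change that. With so few clusters, an ordinary maximum-likelihood GLMM goes wrong in two ways: it underestimates the between-psychiatrist variance, and it refers the statistic to a normal or chi-square distribution as if that variance were known. Both make p-values too small and intervals too narrow.

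An analyst could follow the plan to the letter with a routine large-sample GLMM test and not hold the 5% level. Because the test is left open, it could also be chosen after the data are seen.

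**Working it through.** **1. Inputs.** From Section 9.3: 20 psychiatrists, about 4,000 visits, ICC 0.05 to 0.15, 10% prescribed in Arm 1, 5% type I error, 80% power, detectable Arm 2 rates of 21% and 29%. From Section 4.1: half per arm. Assumed: two-sided test, 10 versus 10 clusters, 200 visits each (4,000/20), no covariates.

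**2. Reproducing the plan's figures.** Design effect = 1 + (200 − 1) × ICC, which is 10.95 at ICC 0.05 and 30.85 at 0.15. Effective size per arm is 2,000/10.95 = 182.6 and 2,000/30.85 = 64.8. Solve for p2 in

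(p2 − 0.10) / sqrt{[0.10 × 0.90 + p2(1 − p2)] / n_eff} = q(0.975) + q(0.80).

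| Quantiles | Sum | ICC 0.05 | ICC 0.15 |
|---|---|---|---|
| Normal | 1.960 + 0.842 = 2.802 | 20.4% | 28.9% |
| t, 18 df | 2.101 + 0.862 = 2.963 | 21.1% | 30.2% |
| Plan | | 21% | 29% |

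A pooled-variance normal calculation gives 20.5% and 29.4%. As a pair, the stated rates fit the normal calculation best, with 20.4% rounded up; t(18) misses the 29%.

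**3. Normal-theory check of the type I error** (20 clusters, 18 df).

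- Wald z with ML variance: the effective critical value is 1.960 × sqrt(18/20) = 1.859, and P(|t18| > 1.859) = 7.9%.
- Wald z with REML-type variance: P(|t18| > 1.960) = 6.6%.
- Likelihood ratio: the critical value is sqrt{18 × [exp(3.841/20) − 1]} = 1.952, giving 6.7%.

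For the first of these the interval half-width is 1.859/2.101 = 0.885 of what it should be, so about 11–12% too narrow.

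**4. Simulation under no effect.** There were 10 + 10 clusters and 8,000 trials per setting (Monte Carlo SE about 0.3 points). The model was a random-intercept logistic GLMM fitted by ML with 15-point adaptive quadrature. The documents do not give smokers per psychiatrist, so 20, 60 and 200 were tried. The true rate is 10% except where shown; 60% is the national screening figure in Section 2.1. Rejection rates in percent:

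| Setting (patients per psychiatrist) | ICC | Wald z | LR | Wald, t(18) | Cluster t-test |
|---|---|---|---|---|---|
| 200, ICC on proportion scale | 0.05 | 7.4 | 6.3 | 5.7 | 4.4 |
| 200, ICC on proportion scale | 0.15 | 7.7 | 6.6 | 5.9 | 3.8 |
| 200, ICC on latent logit scale | 0.05 | 7.2 | 6.0 | 5.6 | 4.5 |
| 200, ICC on latent logit scale | 0.15 | 8.2 | 6.9 | 6.2 | 4.7 |
| 200, beta-distributed rates | 0.05 | 7.6 | 6.6 | 6.0 | 4.8 |
| 200, beta-distributed rates | 0.15 | 7.5 | 6.6 | 5.7 | 4.3 |
| 60 | 0.05 | 8.6 | 7.6 | 6.8 | 5.2 |
| 60 | 0.15 | 7.8 | 7.1 | 6.2 | 4.1 |
| 20 | 0.05 | 7.3 | 6.8 | 5.6 | 5.0 |
| 200, true rate 60% | 0.10 | 7.7 | 6.4 | 5.8 | 4.7 |
| Unequal panels, CV 0.5 | 0.10 | 7.4 | 6.5 | 6.0 | 4.2 |

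The uncorrected tests exceed 5% in every setting: Wald z 7.2–8.6%, likelihood ratio 6.0–7.6%. Moving the ML Wald statistic to t(18) leaves 5.6–6.8%, so changing the reference distribution alone is not a full cure. The cluster-level t-test stays at 3.8–5.2%.

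**5. Aim 3.** The survey target is 20 patients per psychiatrist, and the ICC must be assumed. At ICC 0.05, 20 per cluster and a 10% rate, Wald z rejects 7.3% (table above) and 7.6% in a separate run of 3,000 trials (SE about 0.4 points). At ICC 0.01, with 14 to 20 per cluster and rates of 10–30%, Wald z gives 5.3–5.4% and likelihood ratio 4.9–5.7%, which is close to nominal.

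**The case against.** The strongest reply is that the plan says only GLMM. It does not commit to maximum likelihood, a Wald test or a normal reference, and some software defaults to t or F tests. That is fair. The inflation belongs to an uncorrected implementation, which the plan allows but does not require, so the claim has to be conditional.

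Stronger readings are tempting, and the documents do not support them:

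- **That standard GLMM tests here run at 8–9%.** In the larger simulation only two of 11 settings reached 8%, both with Wald z, and none reached 9%. A smaller run (1,500 trials per setting, SE about 0.7 points) put Wald z at 7.7–9.3%, but that is the worst variant with the less precise estimate.
- **That both stated detectable rates are optimistic, or that they can be obtained only from normal quantiles.** The 21% is within 0.1 points of the t(18) result, and by ordinary rounding 21.1% fits it better than 20.4% does. Only the 29% moves materially.
- **That Aim 3 is affected to the same degree.** Section 9.3 applies its ICC range to prescribing. For abstinence and treatment use none is given, and at 0.01 the problem nearly disappears.

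Stratification is a further uncertainty, and it cuts both ways. If the strata predict psychiatrists' rates and the model ignores them, the test becomes more conservative. If both factors are fitted at two levels each (an assumption), 16 df remain and the normal-theory ML Wald z error rises to 9.9%, because P(|t16| > 1.960 × sqrt(16/20)) = 9.9%. The simulations include no strata.

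**Conclusion.** The concern holds in conditional form. Section 9.2.2 gives no small-sample method for a comparison of about 10 versus 10 psychiatrists. An uncorrected Wald z or likelihood-ratio test of the primary outcomes would have a type I error of roughly 6–8.5% against 5%. The direction is the same in every setting tried at the plan's ICCs; the exact figure depends on the test, the smokers per psychiatrist and the handling of strata. For Aim 3 the same conclusion needs an ICC of about 0.05 or more. The effect on the stated power is small: nothing of note at ICC 0.05, and about 1.2 points (29% to 30.2%) at ICC 0.15.

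This rests on a two-sided test, an equal split and no covariates in the model. It is a moderate error with a cheap remedy, and it matters most for borderline results. Multiplicity across three primary outcomes, and the use of all 4,000 visits for an outcome defined in smokers, are separate matters and are not included in these figures.

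**What to change.** In Section 9.2.2, pre-specify one small-sample-valid source for the confirmatory p-value and confidence interval. Either of these would do:

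- a t-test on psychiatrist-level proportions, with 18 df less those used for strata; or
- a permutation test that re-randomises psychiatrists within the randomisation strata.

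If the GLMM is to stay primary, specify restricted pseudo-likelihood with Kenward-Roger degrees of freedom. That option was not simulated here; the cluster-level t-test was, and it stayed close to or below 5%. State how the strata enter the analysis, apply the same rule to the Aim 3 models, and give an assumed ICC for those outcomes.

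In Section 9.3, restate the detectable rates with 18 df: about 21.1% at ICC 0.05 and about 30.2% at ICC 0.15.

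The cost is a few sentences and a little programming, with no change to conduct or data collection. The downside is slightly wider intervals and a slightly less favourable detectable rate at the upper ICC.

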3. Semi-structured Provider Interviews: Guided by the Proctor and CFIR models, we will conduct semi-structured interviews with 12-14 psychiatrists (6-7 per arm) assessing their views on the appropriateness, acceptability and sustainability of the intervention components, as well as how the clinic’s *inner setting* (e.g., culture, norms, workflow compatibility with the intervention), *outer setting* (e.g., VA policies, psychiatric professional associations), *psychiatrist characteristics* (e.g., beliefs about the intervention), and the *implementation process* (e.g., how providers were informed, who championed the intervention) may impact their views on appropriateness, acceptability and sustainability. We will also ask psychiatrists for their insights into challenges and successes encountered during their participation in the intervention components.

AIM 3 Measures: Patient Use of Cessation Treatment and Self-Reported Abstinence

We will also assess patient use of cessation treatment and tobacco abstinence 6 months after seeing a participating psychiatrist in the two arms. For this aim, we will conduct a follow-up telephone survey with the 400 cluster-sampled patients who completed a post-visit survey during the intervention period. The follow-up survey will ask patients to indicate whether they used a list of tobacco treatments in the prior 6 months, including all FDA-approved cessation medications, in-person cessation counseling, telephone cessation counseling, and a mobile texting cessation service. Consistent with guidelines for measuring abstinence in pragmatic trials, the survey will also assess 7-day point prevalence abstinence.⁴⁸ Using methods that we have successfully used on prior research, we will make up to 10 attempts at different times of the day and month to reach patients by phone for a follow-up survey. Telephone non-respondents will be sent a survey in the mail with a pre-paid return envelope.

Other Measures: Patient Characteristics

Our patient surveys will collect additional information, including sociodemographics (age, gender, marital status, race/ethnicity, income), attitudes toward tobacco treatment using the *Attitudes Toward Nicotine Replacement Therapy Scale*⁴⁹ adapted to ask about NRT and counseling, quitting self-efficacy using the *Smoking Self-Efficacy Questionnaire*,⁵⁰ motivations to quit using a 0-10 scale, and smoking status and history using questions from the California Tobacco Survey.⁵¹

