7.1.1.4 Post-Visit Patient Survey

Patient PHI, including names, phone numbers, mental and physical health information, and tobacco-related measures will be obtained through CPRS and patients who see a participating psychiatrist. Once a month during the 6-month intervention period we will survey a random sample of patients seen by a participating psychiatrist within 24 hours of their visit. The survey

CONFIDENTIAL

will ask patients whether their psychiatrist asked them about their smoking, and offered NRT and counseling, as well as the patient's sociodemographics, smoking behavior, cessation treatment use, and motivation to quit.

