This material is the property of the NYU School of Medicine and NYU Langone Health. Do not disclose or use except as authorized in writing by the study sponsor

from missing data and subject dropout. An IIT approach will be compared with the complete-case only method, but our primary analysis will be the complete case analysis, as The North American Quitline Consortium has found this approach to be more accurate in representing true quit rates and recommends use of this calculation,⁵² as do other reviews.⁵³

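### Aim 3 names no covariates for its complete-case GLMM, so arm differences in patient mix would pass into the abstinence and treatment-use contrasts

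*Combined protocol and SAP*

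**What the plan says.** Section 9.2.2 (Aim 3) classifies each surveyed patient on two outcomes: 7-day abstinence at 6 months, and "having used or not use any type of cessation treatment in the 6 months after their visit". The model is given in one sentence: "We will use GLMMs to compare these two outcomes between groups". No covariate, stratification factor or baseline value is named. Aim 3 is tied to the earlier aim by "We will use a similar analytic approach as in Aim 1", and the Aim 1 text names no covariates either.

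On missing data, the Aim 3 text says "our primary analysis will be the complete case analysis, as The North American Quitline Consortium has found this approach to be more accurate". It also says "An IIT approach will be compared with the complete-case only method" (apparently meaning ITT), without stating how non-respondents count under that approach. The Aim 1 text plans missing-data sensitivity analyses for all analyses, using a separate category or multiple imputation. It does not list the imputation variables.

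The patient data are described in section 5.4, under Other Measures: "Our patient surveys will collect additional information, including sociodemographics (age, gender, marital status, race/ethnicity, income", together with smoking status and history, motivation, self-efficacy and attitudes. Table 2 adds treatment use in the 6 months before the post-visit survey. Section 9.2.1 gives patient characteristics a descriptive role only.

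Sections 3.2 and Table 2 label both Aim 3 outcomes as secondary.

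**The concern.** The justification does not match the use. A method that represents true quit rates well is a method for estimating the level of one rate. Aim 3 estimates a difference between arms, and its second outcome, treatment use, is not a quit rate at all.

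The design also leaves room for the arms to differ in patient mix:

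- There are about 10 psychiatrists per arm, with 20 surveyed patients each (section 5.4).
- Randomisation is stratified by panel size and number of smokers (section 4.1), not by patient-level prognostic factors.
- Patients are selected and surveyed after a visit conducted under the assigned reminder. Smokers are identified through the health record (section 10.3.2), and the plan expects opt-out to increase screening, so the pool of identified smokers could differ by arm.
- All women but only 5 to 10 men per psychiatrist are approached each month, so the sex mix depends on each panel.

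If the arms differ in something that predicts quitting, a model with arm alone reports that difference as part of the reminder's effect. Variables that could absorb some of it are already being collected.

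**Working it through.** **The plan's own figures.** None is given for Aim 3: no expected abstinence, response rate or power. The power figures in section 9.3 (21% and 29% detectable) concern prescribing under Aim 1 and do not bear on this point. The ICC range of 0.05 to 0.15 is borrowed from there. All quit and response rates below are assumptions for illustration.

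**1. Effect of patient mix.** Assume heavy smokers quit at 8% and respond at 60%, others quit at 20% and respond at 80%, identically in both arms, with no true effect. For heavy-smoker share s:

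respondents-only rate = [s × 0.6 × 0.08 + (1 − s) × 0.8 × 0.20] / [s × 0.6 + (1 − s) × 0.8]

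| s | Respondents only | Full response: 0.08s + 0.20(1 − s) |
|---|---|---|
| 0.55 | 0.0984/0.69 = 14.3% | 13.4% |
| 0.45 | 0.1096/0.71 = 15.4% | 14.6% |
| 0.60 | 0.0928/0.68 = 13.6% | 12.8% |
| 0.40 | 0.1152/0.72 = 16.0% | 15.2% |

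The gaps are 1.2 points (55/45) and 2.4 points (60/40) in both columns. Patient mix produces them; restricting to respondents adds essentially nothing here. Adjusting for heaviness removes them, because within each stratum the arms are equal.

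**2. How likely such a split is by chance.** For a trait with 50% prevalence and 200 patients per arm in clusters of 20:

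SD of the arm difference = √[2 × 0.25 × (1 + 19 × ICC)/200]

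- ICC 0.05: design effect 1.95, SD 7.0 points. A difference of 10 points or more occurs in about 15% of trials, 20 or more in 0.4%.
- ICC 0.15: design effect 3.85, SD 9.8 points. The corresponding figures are 31% and 4%.

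So 55/45 is ordinary and 60/40 is rare by chance alone.

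**3. Size relative to the noise.** Assume 15% abstinence, 14 respondents per psychiatrist (140 per arm) and ICC 0.05. The design effect is 1 + 13 × 0.05 = 1.65, and the SE of the difference is √(2 × 0.15 × 0.85 × 1.65/140) = 5.5 points. Gaps of 1.2 and 2.4 points are about 0.2 and 0.4 SE.

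**4. When follow-up loss itself biases the contrast.** Within each arm, take the ratio of response if abstinent to response if not abstinent. The complete-case odds ratio equals the true one multiplied by the opt-out ratio over the opt-in ratio.

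- Loss by arm only (80% v 65%): factor 1.
- Loss by outcome only (85% if abstinent, 70% if not, both arms): factor 1. With true rates of 10% and 15%, respondents show 11.9% and 17.6%; the odds ratio is 1.59, the same as the true one.
- Loss by arm and outcome jointly (opt-in 75/75, opt-out 85/65): factor (0.85/0.65)/(0.75/0.75) = 1.31. A null odds ratio becomes 1.31; with the arms exchanged it becomes 0.65/0.85 = 0.765.
- Loss by a prognostic trait (half of each arm has it; abstinence 20% with it and 5% without): the same response pattern in both arms (60% without, 80% with) gives 13.57% in each arm, odds ratio 1.00. A pattern that differs by arm (70/70 v 55/85) gives 12.5% v (0.55 × 0.05 + 0.85 × 0.20)/1.40 = 14.1%, odds ratio 1.15. Adjustment for the trait removes this.

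**The case against.** The strongest reply is that chance imbalance is not bias. It is random error that the standard error already covers, and the illustrated gaps are well under half a standard error. That stands for imbalance that is purely chance. Two things remain. Selection after the visit, from smokers identified under different reminders, is a possible systematic route to a difference in mix. And in the one trial that is run, pre-specified adjustment corrects the imbalance that actually occurred.

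A second reply is that missing data are already handled. A reader might infer that the plan ignores them or states an unadjusted analysis. The documents support neither: sensitivity analyses by separate category or multiple imputation are planned for all analyses, an ITT comparison is planned for Aim 3, and the model is silent on covariates rather than declared unadjusted. What is open is which variables enter the imputation and how ITT counts non-respondents.

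A reader might also infer that complete-case analysis necessarily biases the arm contrast through follow-up loss. It does not. Loss related to outcome equally in both arms leaves the odds ratio intact, and no document gives a response rate or pattern that would show the harmful kind of loss.

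Finally, it is tempting to fill in treatment use for non-respondents from the health record, since section 7.1.1.4 says "tobacco-related measures will be obtained through CPRS". That would be a mistake. Under section 6.1.2, opt-out orders and referrals generate unless cancelled. Counting them as patient use would favour that arm by construction and repeat primary outcomes 2 and 3.

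**Conclusion.** The point holds as a gap in the model specification for two secondary outcomes. Aim 3 rests on a complete-case GLMM with no named covariates, justified by an argument about the level of quit rates, while prognostic patient data are collected and given no role in the contrast. The trial's primary endpoints are not affected.

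The illustrated size is 1 to 2.5 percentage points of abstinence with no true effect, from heavy-smoker shares differing by 10 to 20 points between arms. This depends wholly on the assumed quit rates and shares. Bias from loss is a conditional risk: an odds ratio of 1.15 to 1.31, or 0.765 in the other direction, under assumed arm-dependent patterns, and none if loss follows only the arm or only the outcome. Covariate adjustment repairs only what the measured covariates explain; loss that depends on arm and outcome beyond them remains.

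**What to change.** Keep respondents as the abstinence data set, and write the following into section 9.2.2 before any arm comparison is seen:

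1. Fit both Aim 3 GLMMs with a random effect for psychiatrist and fixed effects for arm, the randomisation stratification factors, sex, age and smoking history (years smoked, cigarettes per day, assuming the survey's smoking-history items provide them).
2. Do not adjust for motivation, attitudes or self-efficacy. The survey follows the arm-specific visit, so the reminder may already have changed them.
3. Use cigarettes per day and prior-6-month treatment use only for patients with no earlier visit under the reminder; otherwise these too may reflect the arm. If many patients had such a visit, leave both out of the main model. Make that decision from visit dates alone.
4. Use the same variables, and the psychiatrist cluster, in the multiple imputation already planned, and state how the ITT comparison counts non-respondents.
5. Do not count orders or referrals in the health record as treatment use. At most, report them separately.
6. Reconcile sections 10.4.1 and 11.1, which describe surveys without links to identifiable information, with the need to join each patient's post-visit and 6-month surveys. Without that link the adjustment cannot be done.

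The cost is SAP wording, the linkage clarification and a few model parameters. The stratification factors use between-psychiatrist information: with 20 psychiatrists and two arms there are 20 − 2 = 18 degrees of freedom, or 16 if each factor enters as one term. The odds ratio becomes conditional on the covariates, and its standard error need not shrink, so greater precision should not be promised.
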